9.3.1.3. Birth Weight (Including Small for Gestational Age)

All live births will be classified as small, appropriate, or large for gestational age using the CDC definition of birth weight below the 10th percentile, between the 10th and 90th percentile, and above the 90th percentile, respectively. An infant's birth weight percentile and size for gestational age categorization will be based on World Health Organization growth charts or country-specific growth charts, as appropriate. Low birth weight (< 2500 g) will also be examined as an adverse pregnancy outcome.

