9.3.2.4. Pregnancy Outcome Follow-up

It is expected that the registry will collect the following information from the participant's HCP on record, from other practitioners, from electronic medical records, or from the participant, as needed, at approximately 4 weeks after the EDD:

- Pregnancy outcome risk factors
 - Smoking
 - Caffeine use (> 200 mg per day)
 - Alcohol use
 - Recreational drug use
- Weight gain during pregnancy

CONFIDENTIAL

- Nusinersen exposure history and adherence
 - The participant's nusinersen exposure history will be captured with dates for doses prior to and during pregnancy, if not already captured at an earlier timepoint. If the exact dates are unavailable, the HCP or participant will provide the best approximation available (e.g., ± week).
 - Delayed or missed doses (with reason) over the course of the pregnancy
- Other current medications (including folic acid and vitamins)
- Possible SMA symptoms as determined by the HCP (e.g., muscle weakness, change in gait, tremor, respiratory changes) from the Prenatal Follow-Up assessment until the pregnancy outcome
- Pregnancy outcome (e.g., live birth, stillbirth, fetal loss, pregnancy termination [including reason, e.g., related to SMA, nusinersen, other], fetal anomaly)
- Type of delivery (e.g., vaginal, cesarean delivery [C-section]), including whether labor/delivery was induced early and, if applicable, the reason for induction
- Complications during pregnancy (e.g., pre-eclampsia, adverse reaction to medication) or birth (e.g., birth asphyxia) with associated notable dates (e.g., onset, resolution)
- Neonatal illnesses (e.g., prematurity, respiratory dysfunction, birth trauma) that resulted in hospitalization, including any treatments (e.g., drug therapies)
- Infant characteristics
 - Gestational age at birth (in weeks)
 - Sex
 - Weight and length
 - Head circumference
 - Birth order (for multiple births)
 - Apgar scores
 - Breastfeeding status (whether the infant is breastfeeding, bottle-fed, or both, as well as duration of breastfeeding, if applicable)
 - Genetic diagnoses, including SMA
 - Medications
 - Any MCM noted, including description and attribution
- Any untoward medical occurrence related to a pregnancy outcome, including neonatal illnesses, that could constitute an SAE as defined in Section 11 will also be reported.

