9.5. Study Size

The goal of the research initiative is to enroll as many participants with SMA who receive nusinersen during pregnancy (or within the relevant exposure window) as possible. Based on the number of individuals of childbearing potential currently enrolled in the registries or who come of childbearing age over the duration of the study and the number of incident pregnancies observed in the registries to date, the estimated enrollment number over the 10-year study period is 20 pregnancies.

As of August 2024, the UK Adult SMA-REACH registry has approximately 285 genetically confirmed SMA patients with 72 using nusinersen [Walker 2024]. In the SMArtCARE registry, as of May 2021, there were 965 SMA patients enrolled. This includes 147 women of childbearing age, of whom 117 have been treated with nusinersen.

While enrollment may slow over time, some increase in new patients is expected in all of the registries. In addition to newly enrolled patients, younger patients are expected to reach childbearing age over the next few years. Together, these factors should lead to an increase in individuals of childbearing age in the registries, which will increase the likelihood of capturing incident pregnancies.

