9.7.3. Methods of Analysis

Each pregnancy outcome will be classified into the categories described in Section 9.3 and will be collected and reported separately. Data will be presented in aggregate tables in the interim and final reports.

All analyses will be conducted on an overall basis, as well as stratified by earliest trimester of exposure. For MCMs, analyses will be conducted only for participants who have exposure in the first trimester. The prevalence and 95% CIs of spontaneous abortions, MCMs, SGA births, and abnormal postnatal growth and development will be CONFIDENTIAL

The information contained herein may not be used, disclosed, or published without the written consent of Biogen MA Inc.

calculated. Other negative pregnancy outcomes will be similarly examined as the sample size permits. Infants with minor malformations, chromosomal abnormalities, genetic syndromes, positional defects, and prematurity-related defects will be excluded from the primary analyses related to MCM prevalence; these outcomes will be reported in the interim and final reports. Details of the analysis will be provided in the statistical analysis plan.

If sufficient enrollment numbers are obtained, analyses will also be stratified according to maternal age, gestational age at enrollment, medical condition at time of pregnancy that may affect pregnancy outcome (including but not limited to respiratory, neuropsychiatric, metabolic, cardiovascular, infectious, hematological disease or impairment), and other important risk factors (e.g., concurrent medications and substance use).

Demographic information, clinical characteristics, and other potential factors that may affect pregnancy outcome will be described.

The actual date of delivery (not the EDD) will be used in all analyses. EDD will only be used to schedule outreach to HCPs to ascertain the outcome of an expected birth.

For each interim analysis, pregnancy and infant outcomes will be analyzed cumulatively from the beginning of the study.

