9.7.3.1.3. Small for Gestational Age Births

The prevalence of SGA births reported to the study will be calculated by dividing the number of SGA births by the total number of live births. If sufficient enrollment numbers are obtained, analysis of SGA births may be stratified by earliest trimester of exposure, gestational age at enrollment, maternal age, medical condition, and other maternal risk factors, as appropriate. Sensitivity analyses may be performed for SGA births and may be stratified by each trimester, along with these factors, when the sample size allows.

The 95% CIs for SGA birth rates will be calculated based on the binomial distribution. If sufficient enrollment numbers are obtained, SGA birth rates may also be presented in subgroups by the earliest trimester of exposure, gestational age at enrollment, maternal age, medical condition, and other maternal risk factors at enrollment, as appropriate.

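### SGA prevalence is defined over all live births with singletons and multiples pooled; with about 16 infants, one twin pair would noticeably shift the point estimate, and no singleton rate is planned beside it

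*Protocol*

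**What the plan says.** Protocol 9.3.1.3 states that "All live births will be classified as small, appropriate, or large for gestational age", "using the CDC definition of birth weight below the 10th percentile" for the small category, and takes percentiles from "World Health Organization growth charts or country-specific growth charts, as appropriate". Neither a singleton nor a twin reference is named. Section 9.7.3.1.3 then fixes the SGA prevalence as "dividing the number of SGA births by the total number of live births", with a binomial 95% CI.

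Multiple births are foreseen. Section 9.3.2.4 collects birth order for them, and 9.3.2.1 asks about a family history of them. Plurality is nevertheless not named as a restriction, stratum or adjustment. Under 9.7.3, if enrollment is sufficient, analyses will be "stratified according to maternal age, gestational age at enrollment, medical condition at time of pregnancy" and other important risk factors; 9.7.3.1.3 has a similar optional list ending in other maternal risk factors.

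The SGA estimate itself is committed in 9.7.3. Comparison with general-population rates under 9.7.3.2 is optional and rests on point estimates and 95% CIs. On study size, 9.5 says that "the estimated enrollment number over the 10-year study period is 20 pregnancies".

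**The concern.** Twins tend to be smaller than singletons for reasons unrelated to the drug. In a large cohort their share is stable and small. In a cohort of about 16 infants it is either zero or, with one pair, 2 of 16 to 18 infants (12.5% to 11.1%). The pooled SGA rate therefore depends partly on whether a twin pregnancy happens to be enrolled.

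The optional strata are unlikely to help, because they need enrollment that 20 pregnancies will hardly provide. Restriction with a separate listing works at any size. The protocol already takes that approach for major malformations: 9.3.1.4 and 9.7.3 remove chromosomal, genetic, positional and prematurity-related defects from the primary analysis. It has no corresponding step for plurality in SGA. At stake is how far the reported SGA point estimate can be interpreted, since 9.7.1 envisages using prevalence and CI to look for excess risk with nusinersen.

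**Working it through.** **The plan's own figure.** Section 9.5 gives 20 pregnancies. This cannot be rebuilt, because the incident pregnancy counts behind it are not given. The protocol states no expected number of live births and no SGA precision.

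**Inputs from the protocol.** 20 pregnancies (9.5); background miscarriage 15% to 20% (7.1.2); SGA below the 10th percentile (9.3.1.3), hence a nominal 10% in the chart's reference population.

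**Assumptions, not in the protocol.** Twin-pregnancy rate 1.5% to 3.5%; SGA risk per twin q = 0.3 to 0.6; singleton SGA risk 10%.

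1. Expected size: 20 × (1 − 0.20) = 16 and 20 × (1 − 0.15) = 17. This ignores stillbirths, terminations, loss to follow-up and the extra infant from a twin pair.

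2. Chance of at least one twin pair in 16 deliveries, 1 − (1 − p)^16: 21.5% at p = 1.5% and 43.4% at p = 3.5%.

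3. Expected pooled SGA rate given one pair, (0.10 × singletons + 2q) / infants:

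| Infants (singletons + pair) | q = 0.3 | q = 0.6 | both twins SGA |
|---|---|---|---|
| 16 (14 + 2) | 12.5% | 16.3% | 21.3% |
| 17 (15 + 2) | 12.4% | 15.9% | 20.6% |
| 18 (16 + 2) | 12.2% | 15.6% | 20.0% |

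For 16 infants and q = 0.3 this is (1.4 + 0.6)/16 = 12.5%; with both twins SGA it is (1.4 + 2)/16 = 21.3%. For q = 0.3 to 0.6 the inflation is about 1.2 to 1.6 times. If the twins are independent, both are SGA with probability q² = 0.09 to 0.36, and with higher probability if they are positively correlated.

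4. Effect on the interval (exact Clopper-Pearson 95% CI), 14 singletons plus one pair with both twins SGA:

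| SGA singletons | Singletons only | All live births |
|---|---|---|
| 1 | 1/14 = 7.1% (0.2 to 33.9) | 3/16 = 18.8% (4.0 to 45.6) |
| 2 | 2/14 = 14.3% (1.8 to 42.8) | 4/16 = 25.0% (7.3 to 52.4) |

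Both pooled intervals contain 10%. In 16 infants the lower limit first exceeds 10% at 5/16 = 31.3% (11.0 to 58.7). Besides both twins, that needs three SGA singletons of 14, and 3/14 = 21.4% is already about twice the nominal rate.

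**The case against.** A reader might infer that one twin pair doubles the SGA rate and that this would be read as a nusinersen effect. The protocol does not support that. Doubling needs a pair and both twins SGA: jointly about 0.215 × 0.09 = 2% to 0.434 × 0.36 = 16% under the assumptions above, if the twins are independent. In 57% to 78% of such cohorts there is no pair at all. A pair with neither twin SGA lowers the rate, for example from 2/16 = 12.5% to 2/18 = 11.1%. Section 9.7.3.2 reads the interval along with the point estimate, and the comparison may never be made.

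Nor is a systematic bias shown. Averaged over cohorts, twins are 2p/(1 + p) = 3.0% to 6.8% of infants, so the expected shift is about 0.030 × (0.3 − 0.1) = 0.6 to 0.068 × (0.6 − 0.1) = 3.4 percentage points, against intervals some 40 points wide. If the comparator pools multiples, which the protocol does not say, all live births is the matching denominator. The lists of strata are open-ended, country-specific charts are allowed, and the SAP, not shown, may present singletons separately.

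These points stand, and they limit the finding to chance distortion of a small-sample estimate. They do not remove it. The protocol itself fixes the pooled definition, so a singleton main estimate would depart from it. A pooled comparator does not rescue a cohort of this size either: its twin share would be about 3% to 7%, whereas here it is 0% or 11% to 12.5%.

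It would also go too far to say that low birth weight and premature birth are fixed on the same pooled denominator. For the former, 9.3.1.3 says only "Low birth weight (< 2500 g) will also be examined as an adverse pregnancy outcome", and no denominator is set for either.

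**Conclusion.** The point holds as a cheap improvement to a stated method. Section 9.7.3.1.3 commits to one SGA rate over all live births and does not separate multiples, although the data to do so are collected. Under the assumed twin rates there is about a one-in-five to two-in-five chance that the cohort contains a pair. Given a pair, the expected estimate moves from 10% to about 12.5% to 16%, with about 20% to 21% as the upper case.

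The size depends on the assumed twin-pregnancy rate, the assumed SGA risk per twin and a 10% singleton risk. The last is only the chart's nominal rate, since the SGA risk of infants born to mothers with SMA is not given. The result is a less interpretable point estimate, not a demonstrated bias and not a false signal from the interval alone.

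**What to change.** In 9.7.3.1.3, make SGA prevalence among singleton live births the main estimate, keep the all-live-births rate beside it, and list multiple births separately with plurality and outcome. In 9.7.3.2, state that like is compared with like: the singleton rate with a singleton background rate, and the all-births rate with a background that pools multiples. If rates are calculated for low birth weight and premature birth, show them by plurality in the same way. Carry the same wording into the SAP.

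The cost is a slightly smaller denominator for the singleton estimate (for example 14 instead of 16) and one extra table line. No new data are needed and no infant goes unreported.

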9.7.3.1.4. Abnormal Postnatal Growth and Development

The prevalence of abnormal postnatal growth and development reported to the study will be calculated by dividing the number of events of abnormal postnatal growth and development by the total number of live births. If sufficient enrollment numbers are obtained, analysis of abnormal postnatal growth and development may be stratified by earliest trimester of exposure, gestational age at enrollment, maternal age, medical condition, and other maternal risk factors, as appropriate. Sensitivity analyses may be performed for abnormal postnatal growth and development and may be stratified by each trimester, along with the above factors, when the sample size allows.

The 95% CIs for abnormal postnatal growth and development rates will be calculated based on the binomial distribution. If sufficient enrollment numbers are obtained, abnormal postnatal growth and development rates may also be presented in subgroups by

the earliest trimester of exposure, gestational age at enrollment, maternal age, medical condition, and other maternal risk factors at enrollment, as appropriate.

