9.3.1.12. Abnormal Postnatal Growth and Development

Domains of developmental milestones (i.e., social/emotional, language/communication, neurocognitive, movement/physical development milestones) by age up to 52 weeks will be defined by guidelines provided by the CDC [CDC 2020]. As recommended by the

CONFIDENTIAL

CDC, the World Health Organization Growth Charts (suitable for use in the US from birth to 24 months) will be applied for this study, where infant growth measurements will be used to estimate gender-specific weight-for-length, head circumference-for-age, length-for-age, and weight-for-age percentiles.

Postnatal growth deficiency or FTT will be defined as weight in the < 10th percentile for sex and chronological age using international growth reference standards from WHO for children aged 0 to 24 months. Postnatal growth deficiency will be evaluated at 1, 2, 6, 12, 18, and 24 months of age.

Infant developmental deficiency will be defined as failure to achieve developmental milestones for chronological age defined by CDC. Infant developmental deficiency will be evaluated at 1, 2, 6, 12, 18, and 24 months of age.

Developmental milestones will be collected as part of routine clinical practice with pediatrician-determined results of infant status (i.e., below, above, or at age-appropriate achievement) in each of the domains listed above. "Ages and Stages" or similar standardized assessments may be collected for this study if performed as part of routine clinical care. No additional information will be mandated for collection as part of this study.

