9.7.3.1.2. Major Congenital Malformations

The prevalence of MCMs (referred to as birth defects in EUROCAT) reported to the study will be calculated using EUROCAT conventions (http://www.eurocat-network.eu/accessprevalencedata/interpretationguide/calculationofprevalencerates). The prevalence of 1 or more MCMs in addition to the prevalence of specific MCMs will be calculated as follows:

Total Prevalence of Teratologist-Confirmed MCMs = Number of Teratologist-Confirmed Cases / Number of Births (Live and Still)

Other formulas for prevalence may be used to calculate estimates for comparisons to other background rates from other sources.

The analysis of MCM outcomes will be conducted only for participants who have exposure during the first trimester, adjusting for maternal age, medical condition, and other maternal risk factors at enrollment, as appropriate. Sensitivity analyses may be performed for MCMs and may be stratified by each trimester, along with the above factors, when the sample size allows.

The 95% CIs for MCM rates will be calculated based on the binomial distribution.

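### The abnormal growth and development rate divides events by all live births: read literally it is not a proportion and its binomial interval fails, and even as a count of infants it is biased low

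*Protocol*

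**What the plan says.** Protocol Section 9.7.3.1.4 calculates the prevalence by "dividing the number of events of abnormal postnatal growth and development by the total number of live births". For the interval it states: "The 95% CIs for abnormal postnatal growth and development rates will be calculated based on the binomial distribution".

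Section 9.3.1.12 defines two deficiencies, each assessed repeatedly: "Postnatal growth deficiency will be evaluated at 1, 2, 6, 12, 18, and 24 months of age", and "Infant developmental deficiency will be evaluated at 1, 2, 6, 12, 18, and 24 months of age". Development is rated in four domains: "social/emotional, language/communication, neurocognitive, movement/physical development milestones". The growth criterion is a percentile cut-off: "Postnatal growth deficiency or FTT will be defined as weight in the < 10th percentile for sex and chronological age".

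The neighbouring measures count units. Section 9.7.3.1.3 works by "dividing the number of SGA births by the total number of live births". Section 9.7.3.1.2 counts confirmed cases and sets out "The prevalence of 1 or more MCMs in addition to the prevalence of specific MCMs". Section 9.7.3.1.4 has no such rule.

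**The concern.** A binomial interval needs every live birth to score 0 or 1. The formula counts events of conditions that are looked for six times per infant, and no section says that an infant counts once or fixes a single age. Counted literally, a persistently small infant adds one event per visit, and events within an infant are correlated.

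The denominator has a separate fault. It holds all live births, whether or not they were assessed. Contacts are not mandated (Section 9.2.1), incomplete follow-up is expected (Section 9.9), and reports are cumulative and at least annual (Section 9.7.4), so they will include infants too young for later visits. Data collection ends in October 2032 (Section 6), so an infant born after October 2030 cannot reach 24 months within it. Each such infant enters as free of a finding that nobody looked for.

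This is one of the four rates for which Section 9.7.3 promises a prevalence and interval, and Section 9.7.3.2 rests any comparison with background rates on point estimates and intervals. The sponsor receives aggregate tables only (Section 9.4), so if registries count differently, infant-level counts may not be recoverable later.

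**Working it through.** The plan gives no numerical value for this measure, so there is no figure to reproduce. The check applies the formula as written.

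**Inputs**
- Numerator, denominator, interval: Section 9.7.3.1.4.
- Six ages, two deficiencies, four domains, weight cut-off at the 10th percentile: Section 9.3.1.12.
- Live births: 20 pregnancies (Section 9.5) with the general-population miscarriage risk of 15% to 20% (Section 7.1.2) leave 20 × 0.85 = 17 or 20 × 0.80 = 16. I assume 16 and show 12 to 20.
- Assumed: 10% of infants below the weight cut-off at each age, and an exchangeable within-infant correlation of 0 to 0.95 on a latent normal scale.

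**1. Largest number of events per infant.** Two deficiencies × 6 ages = 12. If weight and each of the four domains count separately, (1 + 4) × 6 = 30. The ratio has no upper limit of 1.

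**2. Same infants, two ways of counting (exact 95% CIs).**
- Three of 16 infants below the cut-off at all six ages: 18/16 = 112.5%, for which no binomial interval exists. As infants: 3/16 = 18.8% (4.0% to 45.7%).
- Two such infants: 12/16 = 75% (47.6% to 92.7%). As infants: 2/16 = 12.5% (1.6% to 38.3%).
- Range: three such infants among 12 live births give 18/12 = 150%; four among 20 give 24/20 = 120%.

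**3. Expected value with no drug effect, weight only, if every positive visit is an event.** 6 × 0.10 = 0.60 events per infant, and 16 × 0.60 = 9.6 events, an apparent rate near 60% (exact CI for 10/16: 35% to 85%). At any single visit the reference value is about 10%.

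**4. Behaviour of the interval.** Simulation of 16 infants × 6 visits, weight only, 40,000 studies per row. A study with more events than live births counts as not covered, since it has no interval.

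| Correlation | Events exceed live births | Variance relative to binomial | Coverage, event ratio | Coverage, infants ever affected |
|---|---|---|---|---|
| 0 | 1.4% | 2.25 | 83.2% | 95.9% |
| 0.5 | 7.1% | 5.04 | 63.8% | 97.2% |
| 0.8 | 11.5% | 8.06 | 52.1% | 96.7% |
| 0.95 | 15.0% | 10.88 | 48.8% | 99.3% |

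The nominal 95% interval fails for event counts and holds for infant counts.

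**5. Denominator, counting each infant once.** Suppose 12 of 16 infants are assessed at an age and 3 have the finding. The stated denominator gives 3/16 = 18.8%; infants assessed gives 3/12 = 25.0% (5.5% to 57.2%). If unassessed infants have the same risk, the reported rate is the true rate times the share assessed, here 12/16 = 0.75.

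**The case against.** The strongest reply is that affected infants were meant. The measure is called a prevalence, it is divided by live births, and its interval is binomial. Section 9.7.3.2 also speaks loosely of events when it refers to malformations, which are counted as cases. On that reading a persistently small infant is one case and the interval holds. Section 9.7.3 leaves analysis details to the SAP, the study is descriptive with about 20 pregnancies, comparison with background rates is optional, and an advisory board reviews analyses before interim reports (Section 9.7.5).

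The reading is plausible, but no section states it, and the neighbouring sections show that the protocol can name a unit. The denominator fault survives it. Nor is this a detail merely left open: the protocol itself fixes numerator, denominator and interval.

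Some stronger inferences are tempting, and the documents do not support them:
- A reader might add the five neurobehavioural assessments, reach 35 events per infant, and infer that small-weight findings drown the neurobehavioural signal. Section 9.3 has each variable reported on its own, and Section 9.3.1.13 makes neurobehavioural impairment a separate variable. Only the collection list in Section 9.3.2.5 groups it with milestones.
- A reader might take 60% as the rate the study will report. It arises only if each positive visit is counted.
- Counting each infant once over six visits still gives about 18% to 32% ever below the cut-off with no effect (correlation 0.9 to 0.5). That is a property of any cumulative measure with this cut-off, not of the event wording.

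**Conclusion.** The point holds in two parts. Taken literally, the formula in Section 9.7.3.1.4 conflicts with its own interval: up to 12 events per infant are countable (30 by domain), the ratio can pass 100%, and in the weight-only simulation the 95% interval covered 49% to 83%. Exceeding 100% is a possibility, not a certainty; it occurred in 1.4% to 15% of simulated studies. Taken as affected infants, the interval is acceptable, but the all-live-births denominator pulls the rate down in proportion to the share of infants not assessed.

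The sizes rest on 16 live births (range 12 to 20), a 10% rate per visit taken from the percentile definition, and assumed within-infant correlations. The conflict between event counts and a binomial interval, and the direction of the denominator bias, do not depend on those values. With no decision rule tied to this rate, the harm is a reported figure that cannot be interpreted or compared.

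**What to change.** In Section 9.7.3.1.4, make the numerator the number of infants with the finding, each counted once, and the denominator the number of infants assessed. Report growth deficiency and developmental deficiency separately at each assessment age, with exact binomial intervals. Note beside the growth result that about 10% of a reference population lies below the 10th percentile for weight at any single visit.

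If a figure for ever affected by 24 months is given, count each infant once, account for incomplete follow-up, and treat infant death as a competing event, not as ordinary censoring. Give the same definition to all registries before they prepare aggregate tables.

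The cost is one paragraph of wording and a few more small tables (2 deficiencies × 6 ages = 12 proportions), many with sparse cells. Section 9.3.2.5 already collects the data by visit.
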